3. OBJECTIVES, ENDPOINTS, AND ESTIMANDS

Objectives	Endpoints	Estimands	
Primary substudy objective(s):	Primary substudy endpoint (as secondary endpoints for B7451094):	Primary substudy estimand(s):	
• To evaluate the potential effects of abrocitinib on bone development in adolescent participants 12 to <18 years of age, as assessed by knee MRI.	• The proportion of bone safety findings in knee MRI 1 year after randomization in adolescent participants exposed to abrocitinib 100 mg and 200 mg QD.	• The primary substudy estimand is the incidence of bone safety findings in knee MRI after 1 year of being exposed to abrocitinib in adolescent participants 12 to <18 years of age, regardless of dosing compliance or treatment discontinuation.	

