10.10.2. Substudy Schedule of Activities

Substudy Visit Identifier	Substudy Screening	Substudy Randomization (Baseline)	Substudy Recurring Visit [Week 12 (Day 85 ±3 days), 24 (Day 169 ±7 days), 36 (Day 253 ±7 days)]	Substudy Early Termination/End of Treatment Visit	Substudy Follow-up Visit ^a
	Main Study Screening (Day -28)	Main Study Day 1	Main study [Weeks 2, 4, 8, 12] ^e	Main Study Day 1 + 365 days ± 14 days	ET/EOT + 28 days ±3 days
Informed consent/assent ^b	Х				
Dispense Study Intervention		Х	Х		
Study Intervention Administration		Х	Х	Х	
Study Intervention Accountability			Х	Х	
MRI procedure ^c	Х			Х	
Assess knees of participant for relevant history	Х				
Review Inclusion/Exclusion criteria for the substudy	х				
Monitor if any discontinuation criteria for substudy have been met or not	Х	Х	Х		
Urine Pregnancy Test (for WOCBP only)		Х	Х	Х	Х
Assess for adverse events ^d	Х	Х	Х	Х	Х
Vital Signs	Х	Х	Х	Х	Х

PFIZER CONFIDENTIAL

Page 100

Substudy Visit Identifier	Substudy Screening	Substudy Randomization (Baseline)	Substudy Recurring Visit [Week 12 (Day 85 ±3 days), 24 (Day 169 ±7 days), 36 (Day 253 ±7 days)]	Substudy Early Termination/End of Treatment Visit	Substudy Follow-up Visit ^a
	Main Study Screening (Day -28)	Main Study Day 1	Main study [Weeks 2, 4, 8, 12] ^e	Main Study Day 1 + 365 days ±14 days	ET/EOT + 28 days ± 3 days
Clinical Chemistry, Hematology (including coagulation panel), Lipid Profile ^f	Х		X ^f	Х	
Contraception check ^g	Х	Х	Х	Х	Х
PROs					
HSS Pedi-FABS (1 month recall)	Х	Х		Х	Х
HSS Pedi-FABS (1 year recall)	Х	Х		Х	Х

a. Substudy follow-up visit should occur approximately 28 days after the substudy early termination/end of treatment visit. Note: if any participant requires MRI following the early termination/end of treatment visit, the expectation is that the MRI would be arranged as soon as feasible and that the substudy follow up visit be conducted as close to the stated visit window as possible. It will not be considered a protocol deviation as long as the substudy follow up visit occurs no more than 14 days after the completion of the MRI in such cases.

b. Informed consent and assent (if applicable) for the substudy will be included in the main study ICD or assent. Participants who subsequently reach the age of majority during the study will be required to be reconsented as an adult.

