c. Participants who turn 18 years during the main study will only have baseline MRI. Participants who have completed 3 months of treatment in the main study and turn 18 years of age during the substudy will be required to attend an early termination visit with an MRI scan.

d. AEs and SAEs are recorded/reported as per Section 8.3.

e. Visits corresponding to main visits. Week 12 visit is End of treatment visit for main study. For substudy participants, activities will be performed as per the substudy schedule of activities.

f. Clinical chemistry includes: urea, sCr, sCysC (at Screening only), estimated creatinine clearance, AST, ALT, TBili, alkaline phosphatase. The lipid profile will include total cholesterol, LDL, VLDL, HDL, and triglycerides. Hematology includes: hemoglobin, WBC, neutrophils (%, absolute), lymphocytes (%, absolute), platelets, and coagulation panel (APTT, PT/INR). Laboratory tests with abnormal results may be repeated once during the screening period; the last value will be used to determine eligibility. Fasting lipid profile panel require at least an 8 hour fast. If possible, participants should comply with fasting requirements at those visits detailed above. For all adolescent participants for the substudy, laboratory tests will be performed at Screening, Week 4 and Week 12 as per the main study SoA, as well as at the ET/EOT visit of the substudy.

g. Review and record contraceptive method and results of pregnancy testing. Confirm that the participant is adhering to the contraception method(s) required in the protocol. Refer to Appendix 4 for contraceptive guidance.

Primary substudy objective(s):		Primary substudy endpoint (as secondary endpoints for B7451094):	
•	To evaluate the potential effects of abrocitinib on bone development in adolescent participants 12 to <18 years of age, as assessed by knee MRI.	•	The proportion of bone safety findings in knee MRI 1 year after randomization in adolescent participants exposed to abrocitinib 100 mg and 200 mg QD.

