## PFIZER GENERAL BUSINESS

## 2.1.3. Additional Estimand(s)

The primary substudy estimand is the incidence of bone safety findings in knee MRI after 1 year of being exposed to abrocitinib in adolescent participants 12 to <18 years of age, regardless of dosing compliance or treatment discontinuation. This estimand is defined according to the primary substudy objective and is in alignment with the primary substudy endpoint. It includes the following 4 attributes:

- Population: Patients aged 12 to <18 years with moderate to severe AD, as defined by the substudy inclusion and exclusion criteria;
- Variable: Binary indicator of whether the participant had bone safety findings in knee MRI 1 year after randomization;
- Intercurrent event(s): Dosing compliance or treatment discontinuation is not considered for analysis. All data collected (including data after discontinuation of treatment) are included.
- Population-level summary: Incidence rate of bone safety findings, defined as the number of participants with bone safety findings in knee MRI 1 year after randomization divided by the number of participants that received treatment during the substudy, in each treatment arm.

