#### PFIZER GENERAL BUSINESS

## 3.5.4. Electrocardiograms

Electrocardiograms (ECG) parameters to be summarized include heart rate, PR, QT, QTcF and QRS.

Population	Description
Enrolled	All participants who sign the informed consent document.
Full analysis set (FAS)	All participants randomly assigned to study intervention and who take at least 1 dose of study intervention. Participants will be analyzed according to the treatment arm they are randomized to.
Safety	All participants randomly assigned to study intervention and who take at least 1 dose of study intervention. Participants will be analyzed according to the treatment they actually received.
Substudy analysis set (SAS)	All participants who entered the substudy and who take at least 1 dose of study intervention during the substudy.

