## PFIZER GENERAL BUSINESS

• The incidence rate of bone safety findings in knee MRI, along with the 95% CI will be estimated for baseline and End of Treatment (EOT) in the substudy, for each treatment arm. In addition, the types of bone safety findings will be summarized.

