## **Appendix 2. Data Derivation Details**

### Appendix 2.1. Definition and Use of Visit Windows in Reporting

Visit Label	Target Day	Definition [Day window]
Baseline	Day 1 (Day of first	Last observation prior to and
	dose)	including day of first dose
Week 2	15	Days 2 to 22
Week 4	29	Days 23 to 43
Week 8	57	Days 44 to 71
Week 12	85	Days 72 to 99
Substudy EOT a	366	Days 353 to 380 or observation collected at Early Termination
Substudy Follow-up b	394	Days 381 to 408 or observation collected after Early Termination

Visit windows will be used for efficacy variables.

a. For MRI and HSS Pedi-FABS assessments in the Substudy

b. For HSS Pedi-FABS assessments in the Substudy

If two or more assessments fall into the same window, the assessment closest to the Target Day will be used. If two assessments are equally distant from the Target Day in absolute value, the later assessment will be used.

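### The one-year knee MRI endpoint pools early-termination scans, including those required on exit at 18, and its denominator counts adolescents never re-scanned

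*SAP*

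**What the plan says.** Protocol Section 3 defines the substudy endpoint as "The proportion of bone safety findings in knee MRI 1 year after randomization". Its estimand applies "regardless of dosing compliance or treatment discontinuation".

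The schedule does not give every adolescent a one-year scan:

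- Turning 18 is a substudy discontinuation criterion (Protocol 10.10.7.4), and dosing stops then (10.10.6).
- Those who turn 18 after three months of treatment must have an early-termination visit with an MRI (10.10.2, footnote c).
- For those who turn 18 sooner, the same footnote says: "Participants who turn 18 years during the main study will only have baseline MRI".
- Adolescents who withdraw during the main study should have an MRI within about a month of their last treatment visit (10.10.4).

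SAP Appendix 2.1 gives the Substudy EOT visit a target of Day 366 and the window "Days 353 to 380 or observation collected at Early Termination"; its footnote a applies this row to MRI. SAP 6.3.1 says that the incidence "will be estimated for baseline and End of Treatment (EOT) in the substudy", by arm, and that types of finding will be summarized. SAP 2.1.3 defines the incidence as participants with findings "divided by the number of participants that received treatment during the substudy". The matching analysis set in SAP 4 is "All participants who entered the substudy and who take at least 1 dose of study intervention during the substudy".

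**The concern.** The early-termination half of the window has no lower day limit. A scan after about three months of dosing, or after less for a main-study withdrawal, therefore carries the same value as a scan after a year. The age-18 rule ends both dosing and imaging, so no one-year scan is planned for these participants. They are also the oldest in the substudy, which matters because epiphyseal closure in late adolescence is one of its stated interests.

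No planned table crosses MRI findings with time on drug. The only subset analysis (SAP 6.4) concerns efficacy, and the substudy report listed in SAP 5 does not include it. The exposure categories in SAP 6.5.3, which that report does use, stop at 10 weeks or more, so an 84-day exit and a 365-day completer share a category.

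As SAP 2.1.3 is written, a treated adolescent without a post-baseline MRI adds to the denominator and can never add to the numerator. Both features would tend to lower a safety incidence that may support regulatory submissions.

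**Working it through.** **The plan's own figure.** None exists for the substudy: Protocol 10.10.10.1 gives no sample size. The main-study margin of error of 10% reproduces (1.96 × √(0.25/100) = 9.8 points) but does not bear on this point.

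**Inputs from the documents.** Main-study treatment is 84 days and substudy treatment 365 days. The EOT window opens on Day 353. An age-18 exit allows about 1 month to the visit and about 1 month more to the MRI (Protocol 10.10.7.2).

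**Assumptions.** Let f be the share of adolescents aged 17 at randomization. The documents give no ages. I take f = 1/6, as if ages were spread evenly over 12 to under 18, with a range of 10% to 30%. Birthdays are spread evenly over the year, and other dropout is ignored at first.

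| Quantity | Formula | f = 10% | f = 1/6 | f = 30% |
|---|---|---|---|---|
| Exit at 18 with an MRI | f × (365 − 84)/365 | 7.7% | 12.8% | 23.1% |
| Baseline MRI only | f × 84/365 | 2.3% | 3.8% | 6.9% |
| Exit scan on or after Day 353, no lag | f × 13/365 | 0.4% | 0.6% | 1.1% |
| Same, with about 60 days' lag | f × 73/365 | 2.0% | 3.3% | 6.0% |
| Exit scan before Day 353 | row 1 minus rows 4 and 3 | 5.7% to 7.3% | 9.5% to 12.2% | 17.1% to 22.0% |

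Most age-18 exit scans therefore fall before the one-year window opens.

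**Effect of the denominator alone.** A 10% incidence among those scanned becomes 10% × (1 − baseline-only share): 9.8%, 9.6% and 9.3%.

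**Effect of shorter exposure, if risk rises linearly with time on drug (assumption).** Mean exposure at an age-18 exit is (84 + 365)/2 = 224.5 days. With s the share of post-dose scans that are age-18 exits, the pooled incidence is 1 − s × (1 − 224.5/365) = 1 − 0.385s times the one-year incidence.

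- s = 7.70/97.70, 12.83/96.16 and 23.10/93.10, that is 7.9%, 13.3% and 24.8%.
- The ratios are 0.97, 0.95 and 0.90, so a true 10% reads as 9.7%, 9.5% and 9.0%.
- With the SAP 2.1.3 denominator as well, the ratio is f × (281/365) × (224.5/365) + (1 − f) = 0.95, 0.91 and 0.84, so a true 10% reads as 9.5%, 9.1% and 8.4%.

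**Sensitivity.** If entry ages ran only from 16 to under 18 (f = 50%), the two ratios would be 0.83 and 0.74. Suppose instead that f = 1/6 and a share d of scanned participants leave early for other reasons, evenly over the year. The first ratio becomes (1 − d) × 0.949 + 0.5d, which is 0.90 at d = 10% and 0.81 at d = 30%.

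**The case against.** The strongest reply is that the pooling is disclosed and fits the estimand. The strategy is treatment policy, all collected data are used, and Appendix 2.1 states the early-termination rule openly. SAP 6.3.1 calls its result End of Treatment, not one year. This stands as a reason to keep these participants in the analysis. It does not turn a Month 4 scan into a one-year scan, and the one-year wording remains in the endpoint and in SAP 2.1.3.

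A reader might infer that early and one-year scans cannot be told apart at all. The documents do not support that. Exposure is also summarized in days, and disposition is tabulated. Each potential bone finding is sent individually to the sponsor's safety group within 24 hours (Protocol 10.10.8.1), so the dosing behind a positive case can be traced. The gap is in the aggregate tables.

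A reader might also infer that the analysis set is undefined, because footnote c and Protocol 10.10.6 can suggest a substudy that starts after Week 12. That reading would drop the post-dose scans of early withdrawals. Other text largely settles the matter. All adolescents are enrolled (10.10.4), there is no separate enrolment visit, those who fail the substudy criteria cannot enter the main study (10.10.7.1), and the substudy schedule puts its baseline on main-study Day 1.

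Finally, the effect is modest beside sampling error. Even if all 100 participants per arm were adolescents, the 95% half-width at a 10% incidence would be 1.96 × √(0.1 × 0.9/100) = 5.9 points. The study is descriptive and has no decision rule (SAP 5.1). That limits the weight of the point but does not remove it.

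**Conclusion.** The point holds as a matter of definition and reporting. Early-termination scans enter the Substudy EOT value with no minimum time on drug, only the pooled incidence is planned, and the written denominator counts baseline-only participants as free of findings.

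Under the assumed age mix, about 13% of adolescents (8% to 23%) exit at 18 with an MRI, and about 4% (2% to 7%) have a baseline MRI only. The denominator alone turns 10% into about 9.6%. Linear accumulation of risk would bring the combined figure to about 9.1% (9.5% to 8.4%). The shares rest on an assumed age distribution. The exposure effect also needs risk to grow with exposure, which the documents do not establish.

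It would go too far to conclude that the bone result is seriously biased or that early scans should be excluded. The computed shift is small over the main range, and the estimand calls for these participants to be kept.

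**What to change.** In SAP 6.3.1:

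- Keep the all-available incidence, labelled *last post-baseline MRI at EOT or early termination*.
- Add one row for MRIs linked to the Day 366 visit, including those done up to about a month after it. Linking to the visit keeps completers scanned after Day 380, whom the day window would miss.
- Add one row for early-termination MRIs, supported by a listing of exposure days, reason for exit and finding. A table split by months would be nearly empty: with 30 to 60 adolescents (assumption), 12.8% is only about 4 to 8 age-18 exits over both arms.
- Use participants with a post-baseline MRI as the denominator, amend SAP 2.1.3 to match, and report how many in the substudy analysis set have none.

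In SAP 4, confirm that the substudy starts with the Day 1 dose. In SAP 6.5.3, extend the exposure categories beyond 10 weeks for the substudy report.

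The cost is a few table rows, a listing and short SAP edits, with no new data. The one-year row will have a smaller n and a wider confidence interval than the pooled row.

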Nonclinical bone microscopic finding of decreased primary spongiosa in the metaphysis bone (femur/tibia) region was noted in young rat (comparable human age of ≥12 years) short duration (up to 1 month) repeat-dose toxicity studies. This microscopic long bones finding was transient, nonprogressive and the NOEL exposure margin at which no bone finding was noted was at least 6x the unbound human AUC at the maximum clinical dose of 200 mg QD (the bone finding was noted at $>23\times$). No abrocitinib related clinical observations, macroscopic, or microscopic, by histopathological examination, long bones findings were observed in rats at any dose in the 6-month toxicity study (up to 26x the unbound human AUC at the maximum clinical dose of 200 mg QD) or in young or adult monkeys in any of the toxicity studies up to 9 months in duration (up to $31 \times$ the unbound human AUC at the maximum clinical dose of 200 mg QD). Young monkeys (comparable human age of 8 years and older) are a sensitive nonclinical species for the detection of potential effects on bone growth and development relevant to adolescent humans because: (1) young monkeys have less active growth plates compared to rats of similar age, and (2) the physiologic ambulatory activity and bone biomechanical loading are similar between young monkeys and human adolescents. Therefore, it is unlikely that the observations in the repeat-dose rat toxicity studies have a clinically significant consequence for adolescent humans. In a juvenile rat toxicity study to support using abrocitinib in children <12 years of age, bone findings (decreased femur bone length and width, bone malrotations, macroscopic femoral head and neck abnormalities including occasional long bone fractures) occurred in a time period when femoral bone neck development was still on-going in early postnatal development in these juvenile rats (postnatal day 10; comparable to approximately 3-months human age at dose initiation).²²

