10.10.7.3. Substudy Follow-up Visit

- MRI may be required if any clinically significant finding is identified in knee MRI following the substudy early termination/end of treatment visit or if for any reason MRI was not performed following the end of treatment visit. This MRI, if required, must be performed **prior** to the substudy follow up visit. After the MRI is performed, review if any abnormal knee MRI findings then:
 - Review findings identified by central reader MRI evaluation, and (if relevant) the adjudication report, and arrange any further follow-up and investigation, if relevant and required;
 - Record medical history/adverse event as appropriate.

Note: if any participant requires MRI following the end of treatment visit, the expectation is that the MRI would be arranged as soon as feasible and that the substudy follow up visit be conducted as close to the stated visit window as possible. It will not be considered a protocol deviation as long as the substudy follow up visit occurs no more than 14 days after the completion of the MRI in such cases.

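### The SAP's closest-to-target-day rule applies to knee MRI, so a clear repeat scan prompted by a bone finding can replace the positive end-of-treatment scan in the primary substudy incidence

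*SAP*

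**What the plan says.** SAP Appendix 2.1 gives the substudy EOT row a target of Day 366 and the definition "Days 353 to 380 or observation collected at Early Termination". Footnote a to that row reads "For MRI and HSS Pedi-FABS assessments in the Substudy", so knee MRI is named. The substudy follow-up row (target Day 394) carries footnote b, "For HSS Pedi-FABS assessments in the Substudy", so MRI is not in that row. Below the table come the selection rule, "If two or more assessments fall into the same window, the assessment closest to the Target Day will be used", and the tie rule, "If two assessments are equally distant from the Target Day in absolute value, the later assessment will be used". The same appendix also says "Visit windows will be used for efficacy variables".

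The endpoint these scans feed is one yes/no per participant at 1 year (SAP 2.1.3). It is reported as an incidence at baseline and at EOT by arm (SAP 6.3.1).

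Protocol 10.10.7.3 sets out when a further scan is taken: "MRI may be required if any clinically significant finding is identified in knee MRI following the substudy early termination/end of treatment visit", or if the EOT scan was not done. That scan must precede the substudy follow-up visit and is to be arranged as soon as feasible.

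**The concern.** A rule that picks the scan nearest a target day is harmless when the number of scans has nothing to do with their result. Here it does. A missed EOT scan normally leads to one scan in all, so a second post-dose scan in the window arises mainly because the first showed something. A negative first scan usually has no competitor, while a positive one may have. The selection therefore depends on the outcome and mainly lowers the incidence.

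This is the primary substudy endpoint and a safety endpoint. The protocol's background describes the rat observation that motivated the substudy in these terms: "This microscopic long bones finding was transient, nonprogressive". Study treatment ends at the EOT visit, so a repeat scan would follow the stop of drug. If a drug effect on bone were reversible and visible on MRI, a later scan could show it cleared. The documents do not say whether such an effect would resolve within weeks.

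**Working it through.** **Inputs.** Target Day 366, window Days 353 to 380, closest scan kept, ties to the later scan (SAP Appendix 2.1). EOT visit at Day 1 + 365 days ± 14, and follow-up visit at ET/EOT + 28 days ± 3 (substudy schedule of activities, Protocol 10.10.2). EOT MRI within about 1 month of the visit (Protocol 10.10.7.2).

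**The plan's own figure.** 1 + 365 = 366, which matches the SAP target. The protocol visit window is 366 ± 14 = Days 352 to 380. The SAP window starts one day later.

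**When a repeat wins.** Let the first scan be on day i and the repeat on a later day r ≤ 380. The repeat is used when |r − 366| ≤ |i − 366|.
- If i ≥ 366, no later day qualifies, so the first scan always stands.
- If i < 366, put d = 366 − i. The repeat wins when r ≤ 366 + d, that is, when the delay r − i is at most 2d.

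**Examples.**
- First scan Day 355 (366 − 355 = 11 days from target), repeat Day 375 (375 − 366 = 9): Day 375 is used. If the first scan was on the visit day, the follow-up visit is due on Days 380 to 386, so this repeat fits the schedule.
- First scan Day 360, repeat Day 372: both 6 days from target, so the later one is used.
- First scan Day 366 or later: never displaced.

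**First-scan days exposed, by delay.** 7 days: 10 of 28 (Days 353 to 362). 14 days: 7 of 28 (Days 353 to 359). 21 days: 3 of 28 (Days 353 to 355). 27 days or more: none.

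**Share displaced.** The documents give no distribution of scan days, so these are assumptions. Take repeat delays of 7 to 21 days as equally likely (15 values).

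First, let the first scan be equally likely on each of Days 353 to 380 (28 values), as when the MRI is done on the visit day. The number of winning delays for d = 13 down to 4 is 15, 15, 15, 14, 12, 10, 8, 6, 4, 2, and zero for smaller d. The sum is 101, and 101/(28 × 15) = 101/420 = 24%. Other delay ranges give 90/280 = 32% (5 to 14 days) and 49/392 = 12.5% (14 to 27 days).

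Second, let the MRI follow the visit, with visit days equally likely over Days 352 to 380 and each lag equally likely, keeping the 7 to 21 day repeat:

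| MRI after visit | Displaced, of in-window first scans | Displaced, of all first scans |
|---|---|---|
| same day | 24% | 23% |
| 0 to 7 days | 17% | 15% |
| 0 to 14 days | 11% | 8% |
| 0 to 30 days | 8% | 4% |

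The share falls because later scans land on or after Day 366, where displacement cannot happen.

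**Effect of one lost finding.** Protocol 10.10.10.1 states no substudy sample size. Under assumed arm sizes, one loss moves the estimate from 1/10 to 0/10 (10% to 0%), 1/20 to 0/20 (5% to 0%) or 1/30 to 0/30 (3.3% to 0%). At zero the SAP uses the Clopper-Pearson interval, whose upper limit is 1 − 0.025^(1/n): 30.8%, 16.8% and 11.6%.

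**The case against.** The strongest reply is that the window rule was never meant to choose the scan for this endpoint. The appendix says "Visit windows will be used for efficacy variables", and Protocol 10.10.10.2 plans no efficacy analysis for the substudy. Protocol 10.10.10.3 and SAP 3.3.1 build the endpoint on adjudicated findings, and any finding in the post-dose central read goes to adjudication. SAP 6.3.1 says all collected data are analysed. On that reading an adjudicated finding counts whatever a later scan shows.

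The reading is available, but the text does not secure it. Footnote a names MRI and would have no purpose for MRI if windows did not apply. The all-data wording concerns compliance and discontinuation. The adjudication wording does not say which of two scans supplies the EOT value.

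Four limits do stand.
- Protocol 10.10.8.1 requires bone safety findings to be entered in the CRF, and potential findings in the central read to go on the SAE form within 24 hours. SAP Section 5 puts the AE summaries in the substudy report. The signal is not hidden; any loss is confined to one tabulated proportion.
- Displacement is not loss, because the repeat must also be clear. The documents give no probability for that and do not link the microscopic rat finding to MRI appearance.
- The further MRI is permissive, and a clinically significant finding is not the same category as an adjudicated bone safety finding.
- 24% is near the upper end for a 7 to 21 day repeat.

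A reader might also infer that early terminators are worse placed, since Day 366 lies far ahead and the later scan would always be nearer. The table does not support this. The EOT row takes the observation made at early termination. Observations made after it belong to the follow-up row, which does not cover MRI. A repeat after early termination competes only if it happens to fall in Days 353 to 380.

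**Conclusion.** As written, the SAP permits a positive EOT knee MRI to be replaced by a clear repeat in the primary substudy incidence, and nothing in either document rules this out. Three conditions must all hold: a first scan on Days 353 to 365, a repeat in the window at an equal or smaller distance, and a repeat without the finding. Under the assumed 7 to 21 day delay and uniform timing, the first two conditions are met for about 8% to 24% of in-window first scans followed by a repeat. The lost share is smaller by the unknown chance that the repeat is clear.

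This should be fixed before the substudy analysis. It is an ambiguity with a one-directional risk in a descriptive study without hypothesis tests, not a demonstrated deletion of findings, and confidence is moderate. A reader might infer that the plan erases bone findings from the safety record. It does not, but the headline incidence could disagree with the SAE records.

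**What to change.** In SAP Appendix 2.1 and Section 6.3.1, state that:
1. The closest-to-target rule does not apply to knee MRI.
2. A repeat MRI prompted by a finding never replaces the EOT or early-termination scan.
3. A participant counts as positive if that scan, or a replacement done because it was missed, has an adjudicated bone safety finding.
4. Repeat scans are reported separately as outcome: resolved, persisting or worsened.

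This keeps the endpoint at about 1 year and does not let later scans redefine it. The sentence limiting windows to efficacy variables should be reworded to agree with footnote a.

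The cost is one or two SAP sentences and a listing, with no new data or procedures. The downside for the sponsor is that the reported rate may be slightly less favourable.
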